4.0 Local Number of Subjects

4.1 Indicate the total number of subjects that will be enrolled or records that will be reviewed locally.

Response: 60

4.2 If applicable, indicate how many subjects you expect to screen to reach your target sample (i.e. your screen failure rate).

Response: 75

4.3 Justify the feasibility of recruiting the proposed number of eligible subjects within the anticipated recruitment period. For example, how many potential subjects do you have access to? What percentage of those potential subjects do you need to recruit?

Response:

There are approximately 300 PACE enrollees/members in Eire and Niagara Counties. Among them 50% are having cognitive impairments. Of 150, we expect about 1/2 to 2/3 of them have caregivers who are experiencing challenges in caregiving; therefore 75 to 100 caregivers. The sample size for this study was determined by a power analysis based on the study similar to ours (Kamiya et al., 2014). The effect size found in the article was $d = 0.65$. We will use a directional hypothesis; therefore, we set $\alpha = .05$, and in order to achieve 80% of statistical power, we will need 30 participants in each group, therefore 60 in total. Expecting 25% attrition, we will recruit 75 participants.

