When the detailed challenges were documented, the OTGS may recommend some solutions, if she has, such as educating the process of Alzheimer's disease and suggesting an assistive device, good grip utensils.

At the end of the interview, the participant will be paid \$20.00.

The UB geriatric team including OTs, a gerontologist, and OTGS will brainstorm to develop solutions to identified problems. Within a week, these solutions will be presented to the participant and the OTGS and the participants will decide final solutions that the participant will perform. We use a caregiver-centered approach to facilitate their motivation to continue their care. The proposed approach will emphasize working collaboratively with caregivers to identify challenges and individualized strategies for each caregiver to solve specific problems. This is a different approach from the traditional therapist-client relationship, in which therapeutic prescriptions are made and provided by OTs to their clients.

Agreed-upon solutions will be reported to the PACE, especially if suggestions involve CRs. If assistive devices are needed, the PACE will provide them along with proper training for use.

Example interventions include: (a) didactic education about diseases; (b) the use of errorless techniques to improve assistance for CR's ADL,

IADL, and communication tasks; (c) the use of incentives (e.g., providing a favorite scented shampoo, going for an ice cream after going to a hair stylist, having a snack or short game to prevent going to bed right after dinner); (d) use of the Buffalo Functional Exercise for strengthening (a home-based exercise developed for PACE by the PI and shown to be effective in preventing falls, as reported by the NY Dept. of Health; attached); (e) use of a schedule/calendar on a computer, cell phone and/or blackboard in CR's home to coordinate caregiving tasks for family members; (f) suggesting more frequent PACE daycare visits or use of a nearby PACE-recommended daycare center; and (g) home safety suggestions using the Home Safety Self-Assessment Tool (HSSAT) to prevent falls in CR's home environment. We expect that more customized solutions will arise from this project.

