The PI will spend 0.11 FTE and the Co-I will spend .05 FTE, extra in addition to regular student's project time (3 credits per semester). Since this project is tied with a students' mandatory research group project, students will spend regular time, 3 hours/week and extra 2% for this project for extra record keeping for this research purpose. In addition, a research assistant will spend 0.2 FET for two calendar years. These efforts were justified and accepted by the School and the grant giver.

Describe the availability of medical or psychological resources that subjects might need as a result of anticipated consequences of the human research, if applicable.

NOTE: One example includes: on-call availability of a counselor or psychologist for a study that screens subjects for depression.

Response:

The PACE has medical doctors, nurses, physical therapists, occupational therapists, a speech and language therapist, and a dentist. They will be available when specific relevant questions arise.

13.3 Describe your process to ensure that all persons assisting with the research are adequately informed about the protocol, the research procedures, and their duties and functions.

Response:

We set aside two months prior to start the project to make sure all parties are familiar with the protocol. Each OTGS will be tested by the PI for the procedure and how to communicate with caregivers, methods to collect data.

We will be communicating with rehab directors at the PACE. The PI will explain the protocol in detail to the rehab facility members in two meetings. The protocol has been accepted by three facilities of the PACE prior to submitting the grant proposal.

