16.0 Data Management and Analysis

16.1 *Describe the data analysis plan, including any statistical procedures. This section applies to both quantitative and qualitative analysis.*

Response:

For two hypotheses, we first analyze a linear trend of dependent variables over time. If they are linear, we will use Generalized Estimating Equation to compare the two groups' slopes. A main effect and an interaction effect will be examined. If it is not, we will use Repeated Measures ANOVA with a between-factor. The contrasts within a group and the difference between groups will be performed as post hoc tests. To answer the last research question to find the difference between

the 4-months data and 6 month after intervention (or at 10 months), we will use Repaeated measurs ANVA with a between-factor.

To answer research questions, we will list all challenges for both groups and solutions for the treatment group. The effectiveness of solutions will be evaluated using a Likert Scale (from very effective to not effective at all) and percentages will be reported. For the rate of continued community, living at 4 months will be tabulated for both groups and a chi-square test will be used. The number of falls and emergency visits will be compared for these two groups using Mann Whitney U-test.

The significance level for primary analyses will be set at .05. SPSS 26.0 will be used for statistical analyses.

16.2 If applicable, provide a power analysis.

NOTE: This may not apply to certain types of studies, including chart/records reviews, survey studies, or observational studies. This question is asked to elicit whether the investigator has an adequate sample size to achieve the study objectives and justify a conclusion.

Response:

The sample size for this study was determined by a power analysis based on the study similar to our study (Kamiya et al., 2014). The effect size found in the article was $d = .65$. We will use a directional hypothesis; therefore, we set $\alpha = .05$, and in order to achieve 80% of statistical power, we will need 30 participants in each group, therefore 60 in total. Expecting 25% of attrition, we will recruit 75 participants.

16.3 Describe any procedures that will be used for quality control of collected data.

Response:

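### Several students deliver the intervention, but the power calculation and planned tests allow for no correlation between treated caregivers of the same student; record the student and add a sensitivity analysis

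*Combined protocol and SAP*

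**What the plan says.** **Delivery.** Under section 9.1, a student visits the caregiver, explores the problems in depth and may suggest something at once. A team of occupational therapists, a gerontologist and students then develops candidate solutions. After that, "these solutions will be presented to the participant and the OTGS and the participants will decide final solutions that the participant will perform". Section 19.2 has students demonstrate the methods and caregivers practise them. Under section 3.1 controls receive usual support.

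**Staffing.** Students are always referred to in the plural, and section 13.2 says "students will spend regular time, 3 hours/week". No number of students is given, and no rule links caregivers to students.

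**Sample size.** Section 4.3 states "we will need 30 participants in each group, therefore 60 in total", and section 16.2 repeats it. The basis is d = 0.65, α = .05 and 80% power. On sidedness, section 16.2 says "We will use a directional hypothesis".

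**Analysis.** Section 16.1 says "If they are linear, we will use Generalized Estimating Equation to compare the two groups' slopes", with repeated measures ANOVA as the alternative. Neither includes a student term. Then: "The significance level for primary analyses will be set at .05".

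**The concern.** The treatment is tailored to each caregiver and negotiated in person, so its quality may depend on which student delivers it. If so, treated caregivers seen by the same student have correlated outcomes, while controls have no such delivery effect. This is a partially nested design.

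GEE and repeated measures ANOVA with the caregiver as the unit handle correlation within one caregiver over time. They do not handle correlation between caregivers who share a student. If that correlation is positive, three things follow:

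- The standard error of the arm difference leaves out the between-student variance.
- The nominal .05 is exceeded to some degree.
- A valid test has less power than stated.

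A few unusually strong or weak students could also influence the result without the analysis showing it. If the student's identity is not kept in the data file, this may be impossible to examine afterwards.

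**Working it through.** **Inputs from the documents:** d = 0.65 (so SD = 1), one-sided α = .05, 80% power, 30 per arm (sections 4.3 and 16.2). I take 30 per arm at analysis as given.

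**Assumptions, not in the documents:** k = 4, 6 or 10 students, one student per treated caregiver, student effect in the treatment arm only, ICC 0.02, 0.05 or 0.10.

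**1. The plan's own figure.** n per arm = 2 × (1.645 + 0.842)² / 0.65² = 29.3, rounded up to 30. With 30 per arm, SE = √(2/30) = 0.2582 and power = Φ(0.65/0.2582 − 1.645) = 80.9%. The exact t-test gives 80.0%. The stated figure is therefore the independent-caregiver calculation, with no reserve.

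**2. With clustering in the treatment arm.** Caregivers per student m = 30/k; design effect DE = 1 + (m − 1) × ICC; SE = √(DE/30 + 1/30); power = Φ(0.65/SE − 1.645).

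Example, 6 students and ICC 0.05: m = 5; DE = 1 + 4 × 0.05 = 1.20; SE = √(1.20/30 + 1/30) = 0.2708, which is 4.9% above 0.2582; power = Φ(2.400 − 1.645) = 77.5%.

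**3. Range.** The t column uses the same SE with a t reference on 58 degrees of freedom. Type I error is for a two-sided .05 unadjusted t-test that ignores the student, simulated with 40,000 runs per setting.

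| Students | ICC | DE | SE | Power, normal | Power, t | Type I error |
|---|---|---|---|---|---|---|
| 4 | 0.02 | 1.130 | 0.2665 | 78.7% | 77.8% | 5.7% |
| 4 | 0.05 | 1.325 | 0.2784 | 75.5% | 74.6% | 7.1% |
| 4 | 0.10 | 1.650 | 0.2972 | 70.6% | 69.7% | 9.1% |
| 6 | 0.02 | 1.080 | 0.2633 | 79.5% | 78.7% | 5.3% |
| 6 | 0.05 | 1.200 | 0.2708 | 77.5% | 76.6% | 6.1% |
| 6 | 0.10 | 1.400 | 0.2828 | 74.3% | 73.4% | 7.5% |
| 10 | 0.02 | 1.040 | 0.2608 | 80.2% | 79.3% | 5.0% |
| 10 | 0.05 | 1.100 | 0.2646 | 79.2% | 78.3% | 5.4% |
| 10 | 0.10 | 1.200 | 0.2708 | 77.5% | 76.6% | 6.2% |

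The SE with clustering is 1.0% (0.2608/0.2582) to 15.1% (0.2972/0.2582) larger than the independent one.

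**4. Few students also cost degrees of freedom.** With Satterthwaite degrees of freedom, power at ICC 0.05 is about 69% (4 students), 74% (6) and 77% (10).

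**5. Dependence on the model.** These figures apply to the unadjusted two-group comparison behind the stated sample size, not to the planned longitudinal model. If the comparison were baseline-adjusted with an assumed baseline correlation of 0.6, the total variance left would be 1 − 0.36 = 0.64 and SE = √((0.64 + (m − 1) × ICC)/30 + 0.64/30). One-sided power by the normal formula would then run from 82% (4 students, ICC 0.10) to 93% (10 students, ICC 0.02).

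**The case against.** The case against a stronger claim is good, and much of it stands.

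- **Shared solutions.** A reader might infer that each student devises the solutions alone. Section 9.1 says otherwise: a joint team generates the candidates. The student's part is to describe the problem, settle the choice with the caregiver and demonstrate it. That still leaves room for differences between students, but less.
- **Assignment.** A reader might infer that each student has a fixed set of caregivers. No section says so. If students rotate or share caregivers, a simple nested structure does not fit and the clustering is diluted.
- **Standardisation.** Students train for two months (9.1), are tested by the principal investigator (13.3) and are supervised (13.1). This may lower the ICC, though it does not make it zero.
- **Number of students.** Three hours a week implies several students. With 19 months of enrolment (10.1) it could equally mean many, and then the effect is small.
- **Contact with controls.** If the same students also interview controls, which is not stated, part of any student effect is common to both arms and cancels. Variation in delivery would remain.
- **Power under adjustment.** In the baseline-adjusted case of step 5, every combination tabulated stays above 80% by the normal formula, before any loss of degrees of freedom. It is therefore not established that the trial has less than 80% power.
- **Fragile model.** With perhaps 4 to 6 students in one arm of 30, a student variance is poorly estimated and may come out at zero. This argues against making that model primary, not against reporting it as a sensitivity analysis.

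What remains is that delivery runs through several students, and neither the sample size nor the analysis mentions it.

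**Conclusion.** The point holds as a conditional one. The plan allows for no correlation between treated caregivers who share a student, and its sample size has no margin to absorb any. Under the assumptions listed in the working, one-sided power for the stated calculation is about 70–79% by t-test (71–80% by the normal formula) instead of 80%. The two-sided type I error of the unadjusted caregiver-level test is about 5–9%. With 10 or more students or a very small ICC, the effect is minor.

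The documents do not support saying that outcomes do cluster by student, that the .05 level is exceeded, or that power is below 80%. Each of those needs the number of students, the assignment and the ICC, none of which is given. This is an inexpensive improvement to the plan and not a fatal flaw.

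**What to change.** 1. **Sections 9.1 and 9.2:** state how many students deliver the intervention and how caregivers are assigned to them. For each treated caregiver, record the student who delivered it, or the main one if several did.
2. **Section 16.1:** keep the planned analysis as the main one. Add a pre-specified sensitivity analysis: a mixed model with a student random effect in the treatment arm only and Satterthwaite degrees of freedom. Report it beside the main result, with the estimated student variance.
3. **Sections 4.3 and 16.2:** say that the 80% assumes no student clustering, and give the power for an assumed ICC. For example, at ICC 0.05 with 6 students it is 77.5% by the normal formula and 76.6% by t-test.

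**Cost:** one extra data column, one extra model and a sentence on power, with no extra caregivers. The sensitivity interval will be somewhat wider, and the student variance will be poorly estimated if students are few.

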2.0 Background

2.1 Provide the scientific or scholarly background, rationale, and significance of the research based on the existing literature and how it will contribute to existing knowledge. Describe any gaps in current knowledge. Include relevant preliminary findings or prior research by the investigator.

Response:

Current research shows that caregiver burden is an issue of concern for this population, as the depression that often accompanies burden can be debilitating for caregivers (Dean & Wilcock, 2017; Etters, Goodall, & Harrison, 2007). When caregivers experience high levels of burden, their care recipients are much more likely to be placed in a nursing home (Etters, Goodall, & Harrison, 2007). Levels of caregiver burden are higher if care recipients have dementia (Prinquart & Sorensen, 2007), because these caregivers face more difference challenges than caregivers for older adults without dementia. Caregiver burden tends to be the result of care of a recipient who has impairments in function, behavior, cognition, and/or psychological factors such as depression (Paradise et al., 2014).

Caregivers are often unaware of how to provide care for their care recipients when they are struggling with the symptoms of AD, especially when they are having difficulty with activities of daily living (ADLs : Seehaer, Low, Reppermund, & Brodaty, 2013). Providing support, education, and training to caregivers that address their individual challenges has the potential to decrease the burden felt by caregivers and as a result increases both the caregivers and care recipients quality of life.

Current research identifies specific interventions that are effective. Pharmacological drug interventions for the care recipient have been shown to relieve caregiver burden (Beinart, et. al., 2012). This information, although helpful for understanding the population, is more specific to

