A month after initial assessment, OTGS will contact CRs for follow-up and 2 months later, the posttest will be administered. At 4 months, follow-up interview will occur. The number of home visits (4-6) will vary depending on case. Finally 6 months after the intervention, a phone call will be made, asking the same questions before and the number of falls and emergency visits of care recipients in the past 10 months. After each interview, a participant will be paid \$20. (The total maximum is \$80).

9.2 Describe what data will be collected.

NOTE: For studies with multiple data collection points or long-term follow up, consider the addition of a schedule or table in your response.

Response:

The outcome measures will use established instruments. To measure caregiver burden, 12-item Zarit Burden Interview (ZBI), for depression, 20-item Center for Epidemiology Study-Depression (CES-D) will be used. Positive Aspect of Caregiving has 9 items. Self-esteem and fatigue questions will use a visual analog scale from 1 to 10. In addition, items of activities of daily living (ADL, e.g., eating, dressing, and toileting) and instrumental ADL (IADL, e.g., meal preparation, housekeeping) that caregivers are assisting will be identified. We do not assess or provide interventions for CRs directly, but we ask caregivers about CR's cognitive levels using Global Deterioration Scale, and functional levels using FIM to assess ADL and OARS' IADL. We also ask if care recipients fell or visited an emergency room.

 *9.3 List any instruments or measurement tools used to collect data (e.g. questionnaire, interview guide, validated instrument, data collection form).*

Include copies of these documents with your submission.

Response:

The assessment form is attached.

9.4 Describe any source records that will be used to collect data about subjects (e.g. school records, electronic medical records).

Response:

We will not use other sources or records. But if the cause of cognitive impairment is not clear, we will ask the PACE to provide it for us. This is written in the consent form.

*9.5 Indicate whether or not **individual** subject results, such as results of investigational diagnostic tests, genetic tests, or incidental findings will be shared with subjects or others (e.g., the subject's primary care physician) and if so, describe how these will be shared.*

Response:

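### Baseline care-recipient cognition and function are measured and named as sources of burden, but the analysis uses neither and no randomisation method or stratification factor is stated; prespecifying their use would bring a small gain.

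*Combined protocol and SAP*

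**What the plan says.** Section 2.1 (Background) attributes caregiver burden to the care recipient's impairments, function and cognition among them, and adds: "Levels of caregiver burden are higher if care recipients have dementia". Section 9.1 places questions on the care recipient's cognitive and physical function in the first structured interview, after consent. Section 9.2 names the tools: "cognitive levels using Global Deterioration Scale, and functional levels using FIM to assess ADL", together with OARS items for IADL.

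Section 16.1 compares the two groups' slopes by GEE if the trend is linear, and otherwise uses repeated measures ANOVA with a between-factor. It says "A main effect and an interaction effect will be examined", and lists within-group contrasts and between-group differences as post hoc tests. Community living is compared by chi-square, and falls and emergency visits by Mann-Whitney. No covariate appears anywhere in the section.

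Section 3.1 calls the trial randomised but gives no method, stratification factor or timing of allocation relative to the baseline interview.

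On size, 4.3 states "We will use a directional hypothesis" and d = 0.65, and concludes "we will need 30 participants in each group, therefore 60 in total".

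**The concern.** The trial is small and its sample size leaves no slack, so information already paid for should be used. The protocol itself treats severity as a source of burden, and the eligibility criteria in section 5 set no limits on cognitive stage, so severity may vary widely.

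Two things could be lost. The first is precision: variance that severity explains stays in the error term of any comparison of score levels. The second is balance: with about 30 per arm, simple randomisation can leave the arms visibly different in stage. If that happens and no adjustment was prespecified, a later adjustment will look data-driven. The chi-square and Mann-Whitney comparisons use no baseline information at all.

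**Working it through.** **Inputs from the documents.** d = 0.65 (so SD = 1), directional alpha of .05, 80% power, 30 per arm (4.3 and 16.2).

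**Assumptions, because the documents give no figures.** Variance explained by severity (R²) 5-15%; severity-burden correlation r of 0.3-0.5, with 0.4 used as the single value; correlation ρ between baseline and follow-up burden of 0.5-0.7.

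**1. The plan's own figure.** n per arm = 2(1.645 + 0.842)²/0.65² = 29.3, so 30. Power at 30 per arm is 80.9% by the normal approximation and 80.0% by noncentral t. The stated 30 reproduces as a one-sided figure.

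**2. Chance imbalance, if allocation were unstratified.** SE of a standardised baseline difference = √(2/30) = 0.258. The probability of a difference above 0.3 SD is 2[1 − Φ(0.3/0.258)] = 24.5%; above 0.5 SD it is 5.3%. At r = 0.4, a 0.3 SD imbalance moves a comparison of score levels by 0.3 × 0.4 = 0.12 SD, and 0.12/0.65 is about 18% of the design effect.

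**3. Precision in an unadjusted level comparison.** The effective d becomes 0.65/√(1 − R²) and the equivalent n becomes 30/(1 − R²). Power is by noncentral t, one-sided.

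| R² | Power | Equivalent n per arm |
|---|---|---|
| 0 | 80.0% | 30 |
| 0.05 | 81.8% | 31.6 |
| 0.10 | 83.6% | 33.3 |
| 0.15 | 85.4% | 35.3 |

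**4. The test that carries the hypotheses.** In 200 simulated trials (30 per arm, three visits, complete data, r = 0.4, within-person correlation 0.6), GEE was fitted with group, time and their interaction, with and without a severity main effect. The group-by-time estimates were identical to rounding error and the SE was 0.113 both ways. Only the SE of the group term fell, from 0.244 to 0.222. A severity difference that shifts all visits equally cancels in the interaction, so steps 2 and 3 do not apply to it.

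**5. Gain beyond adjustment for baseline burden.** The residual variance with the baseline score alone is 1 − ρ². Adding severity, correlated r with burden at both times, makes it 1 − (ρ² + r² − 2ρr²)/(1 − r²). Power is Φ(0.65√15/σ − 1.645), where σ is the residual SD.

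| ρ | r | Residual variance, baseline only | Residual variance, plus severity | Power, baseline only | Power, plus severity |
|---|---|---|---|---|---|
| 0.5 | 0.5 | 0.750 | 0.667 | 89.7% | 92.5% |
| 0.6 | 0.4 | 0.640 | 0.610 | 93.3% | 94.3% |
| 0.7 | 0.3 | 0.510 | 0.501 | 97.0% | 97.2% |

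Severity therefore adds between 0.2 and 2.8 points. The baseline score does most of the work: against 80.9% for an unadjusted post-score comparison, it gives 89.7-97.0%.

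**The case against.** The strongest reply is that an unadjusted analysis of a randomised trial is valid, and that its standard error already allows for chance imbalance. Both planned models also include the baseline visit and test change, so stable severity differences drop out. This stands, and it rules out several inferences a reader might draw:

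- **That a chance imbalance in stage feeds directly into the hypothesis tests.** It does so for level comparisons, not for the group-by-time term, unless severity also predicts change.
- **That severity drives the course of burden over follow-up.** Section 2.1 speaks only of the level and sources of burden. Nothing in the documents links severity to change over the study period.
- **That adding the two scales as plain covariates would lift the planned tests from 80% to 82-85%.** Step 4 shows no gain there with complete data.
- **That allocation is unstratified.** Section 3.1 describes no method at all, so stratification is unstated, not excluded.

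The quoted contrast between dementia and no dementia is also weaker support than it looks, because invitations go to caregivers of enrollees with cognitive impairment (8.1).

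The reply does not cover everything. Section 16.1 also examines a main effect and between-group post hoc differences, which do carry severity variance and imbalance. The chi-square and Mann-Whitney tests get no help from a baseline score. The complete-data condition is also unlikely to hold, since 4.3 expects 25% attrition.

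**Conclusion.** The point holds as a modest improvement. The scales are collected at baseline, the protocol's own background gives the reason to use them, and 16.1 leaves them out. The 82-85% power and the 0.12 SD shift are confined to unadjusted level comparisons and rest on an assumed R² of 5-15% and an assumed correlation of 0.4; the shift also presumes unstratified allocation. Once each outcome is adjusted for its own baseline value, the further gain is about 0.2-2.8 power points, again under assumed correlations. The planned group-by-time test gains nothing from a covariate main effect with complete data. The main value of acting now is that the adjustment is fixed before the results are seen.

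**What to change.** In 16.1, prespecify a baseline-adjusted model for burden, depression and the secondary scores: each follow-up score adjusted for its own baseline value, with baseline Global Deterioration Scale stage and FIM ADL total as covariates. If the slope or repeated-measures model is kept, include covariate-by-time terms; these help only to the extent that severity predicts change.

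In 3.1, state the randomisation method and when allocation happens. For caregivers still to be enrolled, and provided the baseline interview precedes allocation, stratify on one two-level Global Deterioration Scale split and carry it into the analysis. The planned chi-square and Mann-Whitney tests cannot take a covariate, so replace them with stratified versions (Cochran-Mantel-Haenszel and van Elteren).

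The cost is a few sentences in the plan, a two-stratum allocation list and a few degrees of freedom. If the interview now follows allocation, stratifying would also need a change in procedure. With about 60 people, strata and covariates should stay this few.
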